8.4. Severity assessment

The severity of adverse events will be assessed according to the NIH Common Terminology Criteria for Adverse Events version 4.0. The generic severity scale is shown in Table 3. NIH CTCAE v4.0 severity scales specific to selected important immune mediated checkpoint inhibitor toxicities are included in Appendix 2.

Table 3. Generic scale for assessing the severity of AEs (CTCAE v4, NIH NCI)

Grade	Description	Definition
1	Mild	Asymptomatic or mild symptoms; clinical or diagnostic observations only; intervention not indicated.
2	Moderate	Minimal, local or noninvasive intervention indicated; limiting age-appropriate instrumental ADL*.
3	Severe	Medically significant but not immediately life-threatening; hospitalization or prolongation of hospitalization indicated; disabling; limiting self care ADL**.
4	Life-threatening	Urgent intervention indicated
5	Death	Death related to AE

*Activities of Daily Living (ADL). Instrumental ADL refer to preparing meals, shopping for groceries or clothes, using the telephone, managing money, etc.

**Self care ADL refer to bathing, dressing and undressing, feeding self, using the toilet, taking medications, and not bedridden.

Participants will be asked to record their temperature on a daily basis, as well as the size of any swelling or redness at the vaccination site and the symptoms that can be associated with checkpoint inhibitor therapy. For these solicited AEs participants will be instructed on self assessment of symptom severity based on the NIH CTCAE criteria above. The measured local reaction and daily temperature recording will be numerically graded in severity according to Table 4:

Table 4. Scale for assessing the severity of solicited AEs with numerical values

Adverse Event	Grade	Intensity
Erythema at injection site	1	≥3 - ≤50 mm
	2	>50 - ≤100 mm
	3	>100 mm
Swelling at injection site	1	>1 - ≤20 mm
	2	>20 - ≤50 mm
	3	>50 mm
Fever (oral)	1	37.6°C - 38.0°C
	2	38.1°C – 39.0°C
	3	>39.0°C

Physical observations taken at rest will be graded according to criteria in Table 4 and acted upon based on clinical context and prior history of the individual.

	Grade 1 (mild) *	Grade 2 (moderate) **	Grade 3 (severe) ***
Tachycardia (bpm)	101 – 115	116 – 130	>130 or
Bradycardia (bpm)	50 – 54	40 – 49	<40
Systolic hypertension (mmHg)	141 - 159	160 – 179	≥180
Diastolic hypertension (mmHg)	91 - 99	100 – 109	≥110
Systolic hypotension (mmHg)	85 – 89	80 – 84 or	<80 or

8.5. Reporting procedures

Reporting Procedures for All Adverse Events

After an eligible participant is enroled onto the study on receipt of the first study procedure, all AEs occurred within 28 days of study treatment and only grade 3 AEs outside this time window will be reported in the study case report forms (CRF), whether or not attributed to study procedures. AEs may be observed by the Investigators or reported by the participant either spontaneously or during diary card monitoring. All AEs that result in a subject's withdrawal from the study will be followed up, with their consent until a satisfactory resolution occurs, or until a non-study related causality is assigned.

Reporting Procedures for Serious Adverse Events

All serious adverse events (SAEs) occurring after an eligible participant is enrolled onto the study on receipt of the first study intervention, will be reported throughout the trial period. All SAEs will be documented accurately and notification deadlines respected. SAEs will be reported on an SAE Report Form to the Sponsor or the Sponsor's delegated representative (Chief Investigator) and the Study Medical Monitor (SMM), according to the relevant SOP within 24 hours of the Investigator becoming aware of them. SAEs will not normally be reported immediately to the ethical committee(s) and MHRA unless there is a clinically important increase in occurrence rate, an unexpected outcome, or a new event that is likely to affect safety of trial volunteers, in the opinion of the Chief Investigator and/or SMM. In addition to the expedited reporting above, the Investigator shall include all SAEs in the annual Development Safety Update Report (DSUR) report. Any updates to relevant information concerning the SAE that becomes available after the SAE initial report has been sent (outcome, precise history, results of investigations, copy of hospital report, etc) will be forwarded in a timely manner using the SAE Update Report Form. For all deaths, any available post-mortem reports and relevant medical reports will be made available for reporting to the relevant authorities. The Sponsor, or a medically qualified investigator delegated by the

Sponsor, is responsible for commencing, maintaining and completing the SAE Sponsor Report Form. The anonymity of subjects shall be respected when forwarding this information.

Expectedness

Expectedness will be determined according to the Investigators' Brochure (ChAOx1.5T4 and MVA.5T4 vaccines) or the SmPC (nivolumab).

Reporting Procedures for SUSARs

The Chief Investigator will report all SUSARs to the MHRA and ethical committee(s) within required timelines (15 days for all SUSARs, unless life threatening in which case 7 days, with a final report within a further 8 days (total 15). The Chief Investigator will also inform all Investigators concerned of relevant information about SUSARs that could adversely affect the safety of participants. All SUSARs and deaths occurring during the study will be reported to the Sponsor.

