4.3. Allocation to study groups and dosing regime

The 36 subjects will be recruited to the study: 12 patients with low- or intermediate-risk prostate cancer (Group 1) and 24 patients with metastatic prostate cancer (Group 2).

Group 1: Low- or intermediate-risk localised or locally advanced prostate cancer patients scheduled to undergo radical prostatectomy

12 subjects will be treated with ChAd-MVA.5T4 vaccination plus 1 dose of the anti-PD-1 monoclonal antibody Nivolumab

Week 0:	ChAdOx1.5T4	2.5×10^{10} vp	intramuscular injection
Week 1:	MVA.5T4	2×10^8 pfu	intramuscular injection
	Nivolumab	480mg	intravenous infusion

Group 2: Metastatic prostate cancer patients with disease progression on anti-androgen therapy with either enzalutamide or abiraterone

24 subjects will be treated with ChAd-MVA.5T4 vaccination plus 3 doses of the anti-PD-1 monoclonal antibody Nivolumab

Week 0:	ChAdOx1.5T4	2.5×10^{10} vp	intramuscular injection
Week 4:	MVA.5T4	2×10^8 pfu	intramuscular injection
	Nivolumab	480mg	intravenous infusion
Week 8:	Nivolumab	480mg	intravenous infusion
Week 12:	ChAdOx1.5T4	2.5×10^{10} vp	intramuscular injection
	Nivolumab	480mg	intravenous infusion
Week 16:	MVA.5T4	2×10^8 pfu	intramuscular injection

Compliance with Dosing Regimen

Administration of all vaccines and checkpoint inhibitor therapies will be undertaken by a delegated research nurse or investigator in the clinical research facility or oncology treatment suite of the respective study centres. All study treatments will be recorded in the CRF and the relevant accountability log by the research nurse or investigator. There are no self-administered investigational products involved in this study.

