4.4. Duration of study

Subjects undergoing radical prostatectomy will all be followed up for a total duration of 6 months from enrolment. Planned follow up for participants with metastatic prostate cancer is 12 months from enrolment.

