Checkpoint inhibitor treatment is associated with immune-mediated adverse reactions which may affect any organ system. Current data on the incidence of immune-related toxicities are derived from a number of large phase III clinical trials administering weeks to months of continuous checkpoint inhibitor therapy until disease progression, loss of clinical benefit or unacceptable toxicity, in a range of non-prostate tumour types. This study, however, will make use of a **restricted course of treatment limited to 3 infusions 4 weeks apart for metastatic PCa patients and only 1 infusion for low- or intermediate- risk PCa patients**. The incidence and severity of immune-mediated toxicities following a limited course of 3 infusions four weeks apart is not publically available. However, immune-mediated adverse events may occur at any time from the onset of therapy or after completion of treatment and may not be dose-dependent. Most immune-related adverse reactions, however, are low in severity and resolve with appropriate management, though fatal cases have been reported.

The frequency and median time to onset for the major immune mediated toxicities from pooled phase III datasets are shown in Table 1. These data relate to continuous therapy regimes with repeat nivolumab infusions at 2 week intervals. The incidence of toxicities grade 3 or above is <2% for all organ systems. Importantly, more than 50% of immune-mediated toxicities develop after several weeks of continuous treatment, therefore the frequency and risk of treatment-related adverse events following a restricted course of 3 infusions in this study is anticipated to be considerably lower than during licenced clinical use.

Table 1. Immune mediated adverse events after continuous monotherapy with Nivolumab

Immune-mediated toxicity	Frequency (%) *		Median (range) time to onset (months)	Corresponding number of doses at median time of onset **
	Any severity	Grade 3 or above		
Rash	25.6	0.9	1.4 months(0.0-113.7)	3
Diarrhoea / Colitis	12.6	1.3	1.4 months (0.0-20.9)	3
Pneumonitis	3.0	0.8	3.3 months (0.0-19.6)	7
Liver dysfunction/ Hepatitis	6.4	1.8	1.9 months (0.0-10.4)	4
Renal dysfunction	2.7	0.5	2.3 months (0.0-18.2)	5
Endocrinopathy				
Thyroid disorders	8.5	<0.1	2.8 months (0.0-14.0)	6

Adrenal insufficiency	0.4	0.2		
Pituitary disorders	0.4	0.2		

* From pooled dataset n = 2227 (CA209066, CA209037, CA209067 trials) nivolumab 3mg/kg across tumour types

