7. ASSESSMENT OF SCIENTIFIC OBJECTIVES

7.1. Primary endpoints and outcome measures

- Incidence of adverse events, using the National Cancer Common Terminology Criteria (version 4) up to 12 months following completion of the study treatment. Adverse events

will be summarized by type and severity in tabular format. Fisher's exact test will be used to compare adverse events rates between study arms.

- Composite response rate for metatstatic PCa patients defined as one of the following:
 - A. PSA response rate:
 - 24-week PSA response rate: Patients who achieve at least a 50% reduction in PSA at 24 weeks compared to baseline.
 - Maximal PSA response rate: Patients who achieve at least a 50% reduction in PSA at any time compared to baseline.
 - B. Reduction of circulating tumor DNA following study treatment:
 - 24-week ctDNA response rate: Patients who achieve at least a 50% reduction in ctDNA at 24 weeks compared to baseline.
 - Maximal ctDNA response rate: patients who achieve at least a 50% reduction in ctDNA at any time compared to baseline.
- Changes in ctDNA from pre-treatment (date of screening/randomization) to post-treatment assessments at any time will be evaluated using a paired t-test. ctDNA will be quantified by digital PCR. Changes in ctDNA will be summarized in terms of means and standard deviations.
- For low- and intermediate-risk PCa patients, serum PSA kinetics secondary to study treatment as measured by rate of change before radical prostatectomy. Serum PSA levels will be measured by a standard clinical laboratory test at baseline and at pre-defined timepoints following study treatment as detailed in Appendix 1.

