APPENDIX 1: SCHEDULE OF ATTENDANCE AND STUDY PROCEDURES

Group 1: Participants scheduled for Radical Prostatectomy

Visit/Telephone Call Number	S	V1	T1	V2	T2	V3	V4		V5	V6
Time from enrolment (weeks +days)	≤ -4	0	0+2	1	1+2	2	5	≥5	16	24
Window (days) *	0		=3	+3	+3	+3	±7	+14	±7	±7
Informed consent	X									
Review of inclusion criteria	X	X								
Review of exclusion criteria	X	X		X		X	X		X	X
Medical history	X	(X)		(X)		(X)	(X)		(X)	(X)
Physical examination	X									
Targeted physical examination		(X)		(X)		(X)	(X)		(X)	(X)
Retrieval of archival diagnostic biopsy		X**								
Fresh biopsy (if required)		X**								
Telephone call			X		X					
Recording vital signs	X	X		X		X	X		X	X
ECOG Status	X								X	X
ChAdOx1.5T4 vaccination		X								
MVA.5T4 vaccination				X						
Nivolumab infusion				X						
Radical Prostatectomy (mpMRI – optional)								X		
Assessment & recording of adverse events		X	X	X	X	X	X		X	X
Patient alert card provided				X						
Diary card provided		A		C						
Diary card returned				X			X			
Haematology ¹	2	2		2		2	2		2	2
Biochemistry ¹	4	4		4		4	4		4	4
Serum glucose ¹	2	2		2		2	2		2	2
Thyroid function tests ^{1,2}	2	2					2			2
PSA ¹	5	5		5		5	5		5	5
Urinalysis	X	X		X		X	X		X	X
HBVsAg, HIV &HCV Ab ¹	5									
Human leukocyte antigen typing (ml)		5								
Exploratory immunology (ml)		50		50		50	50		50	50
Exploratory biochemistry (ml)		2		2		2	2		2	2

Total blood volume per visit (ml) ¹	20	70		65		65	67		67
Cumulative blood volume ≈ 421ml¹									

* Window is based on preceding IMP administration

** Window is -28 days

¹Volume can vary by site according to local practices

² Total triiodothyronine (T3) or free T3c, free thyroxine (T4) and thyroid stimulating hormone (TSH)

Group 2: Participants with Metastatic Prostate Cancer

Table of events (part 1 of 2)

Visit/Telephone Call Number	S	V1	T1	V2	V3	T2	V4	V5	T3	V6
Time from enrolment (weeks+days)	≤-4	0	0+2	2	4	4+2	5	8	8+2	9
Window (days)*			+3	±2	±2	+3	+3	±2	+3	+3
Informed consent	X									
Review of inclusion/exclusion criteria	X	X		(X)	X		(X)	X		(X)
Medical history	X	(X)		(X)	(X)		(X)	(X)		(X)
Physical examination (if required)	X	(X)		(X)	(X)		(X)	(X)		(X)
Retrieval of archival diagnostic biopsy		X ¹								
Fresh biopsy (if required)		X ¹								
Telephone Call			X			X			X	
Recording vital signs	X	X		X	X		X	X		X
ECOG Status	X				X			X		
ChAdOx1.5T4 vaccination		X								
MVA.5T4 vaccination					X					
Nivolumab infusion					X			X		

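### The primary safety endpoint runs to 12 months after treatment, but follow-up stops about 5.3–5.8 months (Group 1) and 8.3 months (Group 2) after the last dose, and all-grade adverse events are collected only to 28 days

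*Protocol*

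**What the plan says.** - **Endpoint.** Protocol 7.1 lists the incidence of AEs "up to 12 months following completion of the study treatment" as a primary endpoint for the whole study, tabulated by type and severity. It adds that Fisher's exact test "will be used to compare adverse events rates between study arms".
- **Follow-up.** Protocol 4.4 says that surgical patients are "followed up for a total duration of 6 months from enrolment". For the other group, "Planned follow up for participants with metastatic prostate cancer is 12 months from enrolment". The synopsis gives the same durations. Section 6.1 counts a patient as enrolled on receiving the first vaccine dose, on day 0.
- **Treatment.** Protocol 4.3 gives Group 1 its last study treatment at week 1. In Group 2, "24 subjects will be treated with ChAd-MVA.5T4 vaccination plus 3 doses of the anti-PD-1 monoclonal antibody Nivolumab"; the dosing table there puts the last nivolumab at week 12 and the last vaccine at week 16.
- **Recording.** Protocol 8.5 states that "all AEs occurred within 28 days of study treatment and only grade 3 AEs outside this time window will be reported" in the case report form. The same section requires serious adverse events to be reported for the whole trial.
- **Schedule.** Appendix 1 has a row headed "Assessment & recording of adverse events", marked at every visit up to the last in both groups, with no grade named.
- **Stated purpose.** Section 9.1 describes the safety report as initial and descriptive. Section 9.2 plans to present frequency, severity and duration.

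**The concern.** Safety is a co-primary objective in both groups, so its endpoint should be one that the visits and the case report form can supply. Three parts of the plan do not fit together. The observation window in 7.1 is longer than the follow-up in 4.4. The severity table in 7.1 needs all grades over the whole window, whereas 8.5 stops collecting non-serious grade 1–2 events 28 days after treatment. The between-arm test has no interpretable contrast.

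A reader of the results could take a table headed as 12-month incidence to mean that patients had been observed for 12 months after treatment. The low-grade counts in it would come from a much shorter period than the grade 3 counts. The late period matters because section 4.6.4 itself says that "immune-mediated adverse events may occur at any time from the onset of therapy or after completion of treatment". A statistical analysis plan cannot repair this, because the protocol fixes both the length of follow-up and what is collected.

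**Working it through.** **Inputs.** Last treatment is at week 1 (Group 1) and week 16 (Group 2), from 4.3. Follow-up ends at 6 and 12 months from enrolment, from 4.4. The last Group 1 visit is at week 24, from Appendix 1. The weeks of the last Group 2 visits cannot be read in the available copy, so the Group 2 end rests on 4.4. One month is 4.348 weeks, so 6 months = 26.1 weeks and 12 months = 52.2 weeks.

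**1. Follow-up after last treatment** = end of follow-up − week of last treatment.

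- Group 1, last visit at week 24: 24 − 1 = 23 weeks = 5.3 months; 12 − 5.3 = 6.7 months short.
- Group 1, 6 calendar months: 26.1 − 1 = 25.1 weeks = 5.8 months; 6.2 months short.
- Group 2: 52 − 16 = 36 weeks = 8.3 months; 3.7 months short.

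**2. Can any reading reproduce the 12 months in 7.1?** None of those tried does.

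- Group 1 with the ±7-day visit window: 5.1 to 5.5 months.
- Group 2 at the late edge of a ±14-day window: 8.7 to 8.8 months.
- Group 2 counted from last nivolumab at week 12: 52 − 12 = 40 weeks = 9.2 months.
- Group 2 if the last visit were nominally at week 48 (an assumption, shown for range): 32 weeks = 7.4 months.

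Reaching 12 months after last treatment would need a last contact at about week 1 + 52.2 = 53 in Group 1 and week 16 + 52.2 = 68 in Group 2.

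**3. All-grade recording under 8.5.** The window closes 4 weeks after the last dose.

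- Group 1: week 1 + 4 = week 5. Share of actual follow-up: 5/26.1 = 19% to 5/24 = 21%.
- Group 2: doses at weeks 0, 4, 8, 12 and 16, each plus 4 weeks, give a continuous window to week 20. Share: 20/52 = 38%.
- Set against the 12 months after treatment in 7.1, the all-grade period is 28/365 = 7.7%.
- Follow-up under the restricted rule: 24 − 5 = 19 weeks (21 weeks on the 6-month reading) in Group 1, and 52 − 20 = 32 weeks in Group 2.

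**4. Grade wording.** The severity scale in 8.4 runs from grade 1 to grade 5. The late rule in 8.5 names grade 3 alone. Serious events are reported throughout and include life-threatening ones, so the literal gap is non-serious grade 4 events.

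**5. The comparison.** Section 9.1 calls the study non-randomised. The two groups differ in disease (localised or locally advanced against metastatic), in nivolumab infusions (one against three), in vaccine cycles (one against two) and in observation after last treatment (5.3–5.8 against 8.3 months). A difference in crude AE proportions could come from any of these.

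**The case against.** The strongest defence is that 7.1 says up to 12 months, that safety reporting is descriptive, and that incidence over the actual follow-up can still be tabulated. Section 7.1 also still speaks of randomisation, so the phrase may simply be left over from an older design. That makes the cause innocent and the remedy easy. It does not rescue the text, because the limit is out of reach for every patient and the available time differs by group.

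A second defence is that little of importance is lost. Serious events are reported throughout, laboratory data are held in the database (10.1), concomitant medication is recorded during follow-up (5.4), and abnormal findings are assessed at any point in the study (8.6). This stands, and it keeps the point modest.

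Three stronger readings are tempting, and the documents do not support them.

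- *Sites hold contradictory instructions.* The Appendix 1 row says when AEs are assessed and recorded but names no grade. Assessing at each late visit and entering only what 8.5 requires satisfies both. The row is silent, not in conflict.
- *The loss falls mainly on Group 1.* Restricted follow-up is 19 × 12 = 228 to 21.1 × 12 = 253 person-weeks in Group 1, against 32 × 24 = 768 in Group 2. About three-quarters (768/1,021 = 75% to 768/996 = 77%) lies in Group 2. The median onset times in Table 1 of section 4.6.4 (1.4 to 3.3 months) all exceed 28 days (0.9 months), but they come from continuous two-weekly dosing and do not show where events would be missed here.
- *Immune-mediated events of every grade must be recorded to the last visit.* That would be a new collection rule. No contradiction in the protocol requires it.

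**Conclusion.** The point holds and should be fixed. The primary safety endpoint states an observation period that the design does not provide: about 6.2–6.7 months too long in Group 1 and 3.7 months too long in Group 2. Its all-grade severity breakdown is collectable only to about weeks 5 and 20. The planned Fisher test of AE rates cannot be interpreted and does not match the descriptive purpose in 9.1 and 9.2.

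A reader might infer that late serious toxicity would go unrecorded; it would not, because 8.5 reports serious events throughout. What is missing is non-serious grade 1–2 events and, on the literal wording, non-serious grade 4 events. How many events that is cannot be derived from the protocol.

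The figures assume treatment on the nominal weeks in 4.3 and, for Group 2, an end of follow-up at 12 months as in 4.4. The alternatives tried move the Group 2 figure between 7.4 and 9.2 months and do not change the conclusion.

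**What to change.** - **7.1, window.** Replace the 12 months after treatment with 6 months from enrolment in Group 1 and 12 months from enrolment in Group 2. State that all-grade incidence covers the period to 28 days after study treatment, and that grade 3 or higher AEs and serious AEs are covered to the end of follow-up.
- **8.5, grades.** Change the late rule to grade 3 or higher.
- **7.1, analysis.** Replace the between-arm Fisher test of AEs with description by group: patients with events by type and severity, with the observation time stated for each grade band.
- **Appendix 1 (optional).** Add a footnote to the AE row pointing to 8.5, as a clarification only.

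These are wording changes. They add no visits and leave treatment untouched. The price is a shorter stated safety window, no formal between-group AE test, and non-serious grade 1–2 events later than 28 days after treatment staying outside the endpoint by an explicit rule. Keeping the 12 months instead would mean extending safety contact to about weeks 53 and 68.
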